11. STATISTICAL CONSIDERATIONS AND DATA ANALYSES

11.1. Hypotheses

In Part 1, the primary endpoints of this study are safety and tolerability; the MTD and RP2D will also be determined. No formal statistical hypotheses will be tested. The primary focus will be on determining the recommended dose for further exploration, the safety profile, and the PK of GSK3326595 in subjects with advanced solid malignancies. Analyses will be descriptive and exploratory.

The primary goal of Part 2 is to evaluate disease-specific clinical activity in subjects with select solid tumors and NHL. The cohorts will be terminated for futility based on interim analysis described in Section 11.9.6.

- For TNBC and ER+BC, efficacy is defined as a clinically meaningful response rate (defined as the percentage of subjects that have achieved a CR or PR) of 25% relative to a 10% historical control response rate.
- For mTCC, efficacy is defined as a clinically meaningful response rate (defined as the percentage of subjects that have achieved a CR or PR) of 30% relative to a 15% historical control response rate.
- For recurrent GBM, efficacy is defined as a clinically meaningful improvement in the rate of subjects who remain progression-free at six months (defined as a 35% six-month PFS rate relative to a 17% historical six-month PFS rate).
- For ACC and HPV-positive solid tumors, efficacy is defined as a clinically meaningful response rate (defined as the percentage of subjects that have achieved a CR or PR) of 30% relative to a 10% historical control response rate.
- For NHL (both p53 wild-type and p53 mutant cohorts), efficacy is defined as a clinically meaningful response rate (defined as the percentage of subjects that have achieved a CR or PR) of 30% relative to a 10% historical control response rate.
- For NSCLC, efficacy is defined as a clinically meaningful response rate (defined as the percentage of subjects that have achieved a CR or PR) of 30% relative to a 10% historical control response rate. An interim futility analysis will be used to determine the scope of further development in this cohort.

The primary goal of Part 3 is to evaluate the safety and tolerability of GSK3326595 in combination with pembrolizumab in solid tumors. No formal statistical hypotheses will be tested.

11.2. mTPI Method

The mTPI design [Ji, 2010] is an extension of the toxicity probability interval method [Ji, 2007] and employs a simple beta-binomial hierarchic model. Decision rules are based on

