14.9.1. Definition of Adverse Events

Adverse Event Definition:

- An AE is any untoward medical occurrence in a subject or clinical investigation subject, temporally associated with the use of a medicinal product, whether or not considered related to the medicinal product.
- NOTE: An AE can therefore be any unfavorable and unintended sign (including an abnormal laboratory finding), symptom, or disease (new or exacerbated) temporally associated with the use of a medicinal product.

Events meeting **AE** definition include:

- Any abnormal laboratory test results (hematology, clinical chemistry, or urinalysis) or other safety assessments (e.g., ECGs, radiological scans, vital signs measurements), including those that worsen from baseline, and felt to be clinically significant in the medical and scientific judgement of the investigator.
- Exacerbation of a chronic or intermittent pre-existing condition including either an increase in frequency and/or intensity of the condition.
- New conditions detected or diagnosed after study treatment administration even though it may have been present prior to the start of the study.
- Signs, symptoms, or the clinical sequelae of a suspected interaction.
- Signs, symptoms, or the clinical sequelae of a suspected overdose of either study treatment or a concomitant medication (overdose per se will not be reported as an AE/SAE unless this is an intentional overdose taken with possible suicidal/self-harming intent. This should be reported regardless of sequelae).
- "Lack of efficacy" or "failure of expected pharmacological action" per se will not be reported as an AE or SAE. However, the signs and symptoms and/or clinical sequelae resulting from lack of efficacy will be reported if they fulfil the definition of an AE or SAE.
- The signs and symptoms and/or clinical sequelae resulting from lack of efficacy will be reported if they fulfil the definition of an AE or SAE. Also, "lack of efficacy" or "failure of expected pharmacological action" also constitutes an AE or SAE.

Events NOT meeting definition of an AE include:

- Any clinically significant abnormal laboratory findings or other abnormal safety assessments which are associated with the underlying disease, unless judged by the investigator to be more severe than expected for the subject's condition.

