- The disease/disorder being studied or expected progression, signs, or symptoms of ٠ the disease/disorder being studied, unless more severe than expected for the subject's condition.
- Medical or surgical procedure (e.g., endoscopy, appendectomy): the condition that leads to the procedure is an AE.
- Situations where an untoward medical occurrence did not occur (social and/or ٠ convenience admission to a hospital).
- Anticipated day-to-day fluctuations of pre-existing disease(s) or condition(s) present or detected at the start of the study that do not worsen.

14.9.2. **Definition of Serious Adverse Events**

If an event is not an AE per definition above, then it cannot be an SAE even if serious conditions are met (e.g., hospitalization for signs/symptoms of the disease under study, death due to progression of disease, etc).

Serious Adverse Event (SAE) is defined as any untoward medical occurrence that, at any dose:	
a. Results in death	
b. Is life-threatening	
NOTE:	
The term 'life-threatening' in the definition of 'serious' refers to an event in which the subject was at risk of death at the time of the event. It does not refer to an event, which hypothetically might have caused death, if it were more severe.	
c. Requires hospitalization or prolongation of existing hospitalization	
NOTE:	
• In general, hospitalization signifies that the subject has been detained (usually involving at least an overnight stay) at the hospital or emergency ward for observation and/or treatment that would not have been appropriate in the physician's office or outpatient setting. Complications that occur during hospitalization are AEs. If a complication prolongs hospitalization or fulfills any	

- other serious criteria, the event is serious. When in doubt as to whether "hospitalization" occurred or was necessary, the AE should be considered serious.
- Hospitalization for elective treatment of a pre-existing condition that did not ٠ worsen from baseline is not considered an AE.

d. Results in disability/incapacity

NOTE:

- The term disability means a substantial disruption of a person's ability to conduct normal life functions.
- This definition is not intended to include experiences of relatively minor medical significance such as uncomplicated headache, nausea, vomiting, diarrhea, influenza, and accidental trauma (e.g. sprained ankle) which may interfere or prevent everyday life functions but do not constitute a substantial disruption

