All COVID-19 assessments and symptom assessments for subjects with COVID-19 adverse events will be summarized based on all recorded AEs. There will be no separate definition of "treatment-emergent" AEs.

All AEs will be listed. A listing of subject numbers for individual adverse events will be provided.

A listing of adverse events recorded as dose-limiting toxicities for Part 1 subjects will be provided. Additionally, a summary of the number of patients experiencing DLTs for Part 1 subjects will be provided.

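### Protocol 14.9.1 says in adjacent bullets that lack of efficacy is not, and is, an adverse event; nothing in either document says which governs

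*Protocol*

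**What the plan says.** Protocol 14.9.1 has two consecutive bullets on the same subject in its list of events that meet the AE definition.

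- The first says that lack of efficacy, or failure of the expected pharmacological effect, "per se will not be reported as an AE or SAE". It adds that signs, symptoms or sequelae arising from it are reportable if they meet the definition themselves.
- The second repeats the rule on signs, symptoms and sequelae: these "will be reported if they fulfil the definition of an AE or SAE". It then ends by saying that lack of efficacy itself "also constitutes an AE or SAE".

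The companion list of events that do not meet the AE definition excludes the disease under study and its expected course. Its wording runs "the disease/disorder being studied, unless more severe than expected for the subject's condition". Protocol 14.9.2 makes seriousness depend on this definition: "If an event is not an AE per definition above, then it cannot be an SAE even if serious conditions are met".

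On the analysis side, SAP 8.1.1.2 lists all AEs and tabulates them by preferred term. It sets no treatment-emergent subset ("There will be no separate definition of" that category) and has no rule for lack-of-efficacy terms.

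**The concern.** A site that follows the second bullet and enters lack of efficacy as an AE complies with the protocol. So does a site that follows the first bullet and enters nothing. AEs and SAEs are the primary endpoints of Parts 1 and 3 and a secondary endpoint of Part 2. Differences between sites in reading the definition would pass into the AE tables by dose and cohort without reflecting any difference in safety.

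Two features of the plan make this more than a matter of tidiness.

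- The SAP counts an AE with missing relatedness as treatment-related (8.1.1.2 and 15.7.2), so such an entry can reach the related-AE tables.
- After Amendment 8, AEs leading to treatment discontinuation are among the few items still sent to the sponsor (Protocol 4.1, 8 and 9.2). Whether stopping for lack of benefit counts as one depends on which bullet the site reads.

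**Working it through.** **Step 1. Are the two bullets really in conflict?** Both are current text in the same list. Both name the same two terms and apply to all subjects. Neither carries a condition, a date or a rule of precedence. They agree on resulting signs, symptoms and sequelae. They disagree only on lack of efficacy in itself: the first says not reported, the second says AE or SAE.

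**Step 2. Does other text resolve it?**

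| Place | What it covers | Does it settle the conflict? |
|---|---|---|
| Protocol 14.9.1, events not meeting the definition | The disease under study and its expected progression, signs or symptoms | In part. It supports omitting ordinary non-response, but does not name lack of efficacy and sits badly with the second bullet |
| Protocol 14.9.2 | An event that is not an AE cannot be an SAE | No. It carries the ambiguity into SAE status |
| Protocol 9.1 and 9.2 | Refer to Appendix 9 for definitions and set collection periods | No |
| SAP 8.1.1.2 and 8.1.1.3 | Tabulate and list what is recorded | No. A treatment-emergent filter would not help either, because such an entry would arise on treatment |

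**Step 3. How large could the effect be on the most literal reading?** The only response benchmarks are those for Part 2 in Protocol 11.1 (for TNBC and ER+BC, for example, "25% relative to a 10% historical control response rate"). Maximum cohort sizes are in SAP Table 2. GBM is left out because its primary endpoint is six-month PFS. Expected non-responders = maximum n × (1 − response rate).

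| Cohort | Max n | Target / historical rate | Non-responders at target | At historical |
|---|---|---|---|---|
| TNBC | 32 | 25% / 10% | 24.0 | 28.8 |
| ER+BC | 35 | 25% / 10% | 26.25 | 31.5 |
| mTCC | 40 | 30% / 15% | 28.0 | 34.0 |
| ACC capsule | 38 | 30% / 10% | 26.6 | 34.2 |
| ACC tablet | 50 | 30% / 10% | 35.0 | 45.0 |
| HPV+ | 28 | 30% / 10% | 19.6 | 25.2 |
| NHL, two cohorts of 25 | 50 | 30% / 10% | 35.0 | 45.0 |
| NSCLC | 15 | 30% / 10% | 10.5 | 13.5 |
| Total | 288 | | 204.95 | 257.2 |

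204.95 / 288 = 71%, and 257.2 / 288 = 89%. The first bullet makes none of these subjects an AE for lack of efficacy alone. The second, taken literally and before the disease exclusion, could cover all of them. The counts assume full cohorts, which did not all occur: SAP 3.1.7 records that NSCLC had fewer than 10 subjects when enrolment ceased.

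**Step 4. Which decisions use these counts?** Part 1 escalation uses the DLT criteria in Table 1 of Protocol 4.2.4.1. Part 3 stopping uses the listed drug-related toxicities in 4.4.4.1. A bare lack-of-efficacy entry is none of these. Protocol 5.4.7 has a broader rule that refers to clinically significant adverse events in more than one third of subjects. It is discretionary, however, and recruitment has ended. ORR is unaffected.

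**The case against.** The strongest reply is that the practical effect is probably small. A tumour that persists or grows as expected is the disease being studied, and the protocol lists that among events that are not AEs. Section 14.9.2 gives death from disease progression as an example of something that cannot be an SAE. A site has explicit grounds not to report ordinary non-response, and neither document shows that any site has reported it. This stands as a limit on size. It does not remove the contradiction, because the exclusion never mentions lack of efficacy and the second bullet states the opposite without qualification.

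A reader might infer from the 71% to 89% that most non-responders could appear as AEs. The documents do not support that as an estimate. Non-response under ORR includes stable disease and missing response (Protocol 11.10.2.3), and Protocol 4.3.1 describes stable disease over several assessments as clinical benefit. Treatment continues until progression, not until a failure to respond. Nowhere is non-response equated with lack of efficacy. The benchmarks also belong to Part 2, where safety is secondary; Parts 1 and 3 have none.

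A reader might also infer a large effect on SAEs. Absence of response alone meets none of the specific outcome criteria in 14.9.2. The 24-hour duty in Protocol 9.2 applies to all SAEs, related or not, so relatedness does not limit it, but a seriousness criterion is still needed first.

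Finally, with recruitment closed, a change in the protocol wording alone has little prospective value. That is fair, and it is why the check on data already recorded matters more.

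**Conclusion.** The point holds as a minor internal inconsistency; it is not a design choice. As written, the protocol gives two opposite instructions on whether lack of efficacy is an AE, and nothing in the protocol or SAP says which applies. AE counts in all three parts, and the post-Amendment 8 reports of AEs leading to discontinuation, can therefore vary by site.

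The size of that variation cannot be derived from the documents. The figure of 71% to 89% is an upper bound for the Part 2 response-rate cohorts only. It assumes full enrolment, the protocol's own response rates, every non-responder treated as lack of efficacy, and no use of the disease exclusion. The true effect may be zero if no site entered such a term. Dose decisions are largely protected by their own toxicity criteria.

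**What to change.** 1. In Protocol 14.9.1, delete the final sentence of the second bullet, the one that ends "also constitutes an AE or SAE". Keep the first bullet and the rule that resulting signs, symptoms or sequelae are reported when they meet the definition. No safety information is lost, because that rule stays.
2. Tell sites with subjects still on treatment how this applies to AEs leading to discontinuation. A note in the study reference manual would be enough.
3. Before the final tables, search the recorded AEs for terms such as lack of efficacy or drug ineffective, query them, and handle them in the same way at every site. State the handling in the SAP or the study report.

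The cost is one sentence of protocol or manual text, one data-management query, and a line in the analysis documentation.

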14.9.3. Definition of Cardiovascular Events

Cardiovascular Events (CV) Definition:

Investigators will be required to fill out the specific CV event page of the CRF for the following AEs and SAEs:

• Myocardial infarction/unstable angina

- Congestive heart failure
- Arrhythmias
- Valvulopathy
- Pulmonary hypertension
- Cerebrovascular events/stroke and transient ischemic attack
- Peripheral arterial thromboembolism
- Deep venous thrombosis/pulmonary embolism
- Revascularization

14.9.4. Recording of AEs and SAEs

AEs and SAE Recording:

- When an AE/SAE occurs, it is the responsibility of the investigator to review all documentation (e.g., hospital progress notes, laboratory, and diagnostics reports) relative to the event.
- The investigator will then record all relevant information regarding an AE/SAE in the CRF
- Post Protocol Amendment 8 implementation, SAEs, AESIs, AEs leading to treatment discontinuation and overdoses (as defined in Section 14.9.1) will be recorded via a paper process and provided to GSK (refer to SRM)
- It is **not** acceptable for the investigator to send photocopies of the subject's medical records to GSK in lieu of completion of the GSK, AE/SAE CRF page.
- There may be instances when copies of medical records for certain cases are requested by GSK. In this instance, all subject identifiers, with the exception of the subject number, will be blinded on the copies of the medical records prior to submission to GSK.
- The investigator will attempt to establish a diagnosis of the event based on signs, symptoms, and/or other clinical information. In such cases, the diagnosis will be documented as the AE/SAE and not the individual signs/symptoms.
- Subject-completed Value Evidence and Outcomes questionnaires and the collection of AE data are independent components of the study.
- Responses to each question in the Value Evidence and Outcomes questionnaire will be treated in accordance with standard scoring and statistical procedures detailed by the scale's developer.
- The use of a single question from a multidimensional health survey to designate a cause-effect relationship to an AE is inappropriate.

14.9.5. Evaluating AEs and SAEs

Assessment of Intensity

The investigator will make an assessment of intensity for each AE and SAE reported during the study and will assign it to one of the following categories in accordance with the National Cancer Institute Common Terminology Criteria for Adverse Events (NCI-CTCAE) Version 4.0:

- Grade 1: Mild; asymptomatic or mild symptoms; clinical or diagnostic observations only; intervention not indicated.
- Grade 2: Moderate; minimal, local or non-invasive intervention indicated; limiting age appropriate instrumental Activities of Daily Living (ADL)¹
- Grade 3: Severe or medically significant but not immediately life-threatening; hospitalization or prolongation of hospitalization indicated; disabling; limiting self-care ADL²
- Grade 4: Life-threatening consequences; urgent intervention indicated.
- Grade 5: Death related to AE.
- 1. Instrumental ADL refer to preparing meals, shopping for groceries or clothes, using the telephone, managing money, etc.
- 2 Self care ADL refer to bathing, dressing and undressing, feeding self, using the toilet, taking medications, and not bedridden.

Assessment of Causality

- The investigator is obligated to assess the relationship between study treatment and the occurrence of each AE/SAE.
- A "reasonable possibility" is meant to convey that there are facts/evidence or arguments to suggest a causal relationship, rather than a relationship cannot be ruled out.
- The investigator will use clinical judgment to determine the relationship.
- Alternative causes, such as natural history of the underlying diseases, concomitant therapy, other risk factors, and the temporal relationship of the event to the study treatment will be considered and investigated.
- The investigator will also consult the Investigator Brochure (IB) and/or Product Information, for marketed products, in the determination of his/her assessment.
- For each AE/SAE the investigator must document in the medical notes that he/she has reviewed the AE/SAE and has provided an assessment of causality.
- There may be situations when an SAE has occurred and the investigator has minimal information to include in the initial report to GSK. However, it is very important that the investigator always make an assessment of causality for every event prior to the initial transmission of the SAE data to GSK.
- The investigator may change his/her opinion of causality in light of follow-up

information, amending the SAE data collection tool accordingly.

• The causality assessment is one of the criteria used when determining regulatory reporting requirements.

Follow-up of AEs and SAEs

- The investigator is obligated to perform or arrange for the conduct of supplemental measurements and/or evaluations as may be indicated or as requested by GSK to elucidate as fully as possible the nature and/or causality of the AE or SAE.
- The investigator is obligated to assist. This may include additional laboratory tests or investigations, histopathological examinations or consultation with other health care professionals.
- If a subject dies during participation in the study or during a recognized follow-up period, the investigator will provide GSK with a copy of any post-mortem findings, including histopathology.
- New or updated information will be recorded in the originally completed CRF.
- The investigator will submit any updated SAE data to GSK within the designated reporting time frames.

14.9.6. Reporting of SAEs to GSK

SAE reporting to GSK via electronic data collection tool

- Primary mechanism for reporting SAEs to GSK will be the electronic data collection tool. Post Protocol Amendment 8 implementation, SAEs will be collected via paper process and submitted to GSK (refer to SRM).
- If the electronic system is unavailable for greater than 24 hours, the site will use the paper SAE data collection tool and e-mail it to the Medical Monitor
- Site will enter the serious adverse event data into the electronic system as soon as it becomes available.
- After the study is completed at a given site, the electronic data collection tool (e.g., InForm system) will be taken off-line to prevent the entry of new data or changes to existing data
- If a site receives a report of a new SAE from a study subject or receives updated data on a previously reported SAE after the electronic data collection tool has been taken off-line, the site can report this information on a paper SAE form or to the Medical Monitor by telephone.
- Contacts for SAE receipt can be found at the beginning of this protocol on the Sponsor/Medical Monitor Contact Information page.

14.10. Appendix 10: Collection of Pregnancy Information

- Investigator will collect pregnancy information on any female subject, who becomes pregnant while participating in this study
- Information will be recorded on the appropriate form and submitted to GSK within 24 hours of learning of a subject's pregnancy.
- Subject will be followed to determine the outcome of the pregnancy. The investigator will collect follow up information on mother and infant, which will be forwarded to GSK. Generally, follow-up will not be required for longer than 6 to 8 weeks beyond the estimated delivery date.
- Any termination of pregnancy will be reported, regardless of fetal status (presence or absence of anomalies) or indication for procedure.
- While pregnancy itself is not considered to be an AE or SAE, any pregnancy complication or elective termination of a pregnancy will be reported as an AE or SAE.
- A spontaneous abortion is always considered to be an SAE and will be reported as such.
- Any SAE occurring as a result of a post-study pregnancy which is considered reasonably related to the study treatment by the investigator, will be reported to GSK as described in Appendix 9. While the investigator is not obligated to actively seek this information in former study participants, he or she may learn of an SAE through spontaneous reporting.

Any female subject who becomes pregnant while participating will discontinue study medication

For male study subjects:

- Investigator will attempt to collect pregnancy information on any female partner of a male study subject who becomes pregnant while participating in this study.
- After obtaining the necessary signed informed consent from the female partner directly, the investigator will record pregnancy information on the appropriate form and submit it to GSK within 24 hours of learning of the partner's pregnancy
- Partner will also be followed to determine the outcome of the pregnancy. Information on the status of the mother and child will be forwarded to GSK.
- Generally, follow-up will be no longer than 6 to 8 weeks following the estimated delivery date. Any termination of the pregnancy will be reported regardless of fetal status (presence or absence of anomalies) or indication for procedure.
- Post Protocol Amendment 8, pregnancy information will be collected up to 90 days after last dose of study treatment via paper process and submitted to GSK (refer to SRM).

